1 PROTOCOL SYNOPSIS

Protocol Title	A Prospective, Multi-center, Randomized, Controlled, Masked, Post-market Study of use of the OMNI® Surgical System in Combination with Cataract Extraction in Open Angle Glaucoma [REDACTED]
Protocol ID Number	[REDACTED]
Study Device	OMNI® Surgical System
Control Group or Device	[REDACTED]
Study Objective	First, to prospectively compare the clinical effect of the transluminal viscoelastic delivery and trabeculotomy using the OMNI Surgical System to the [REDACTED] used with Cataract Extraction in eyes with open angle glaucoma (OAG) and second, to prospectively compare the clinical effect of the transluminal viscoelastic delivery using the OMNI Surgical System to the [REDACTED] used with Cataract Extraction in eyes with open angle glaucoma (OAG)
Study Design	Randomized, controlled, multi-center, post-market prospective study
Primary Effectiveness Endpoint	Primary inference will be based on a planned analysis when all subjects have completed the 12-month visit. 
 Mean change in unmedicated DIOP from baseline at the 12-month postoperative examination
Other Effectiveness Endpoints	
 Proportion of eyes with a \geq 20% decrease in unmedicated mean diurnal IOP (DIOP) from baseline Proportion of eyes with unmedicated mean DIOP between 6 and 18 mmHg inclusive Mean change in the number of ocular hypotensive medications compared to Screening Percent change in unmedicated DIOP from baseline
Safety Endpoints	
 Rates of ocular adverse events (intraoperative, postoperative) Reduction in best corrected distance visual acuity (BCVA) from baseline (note: reduction in BCVA due to posterior capsular opacity (PCO) will not be treated as a safety event) Secondary Ocular Surgical Interventions, including laser, for IOP control

Inclusion Criteria	
At least one eye of each participating subject should meet inclusion criteria.
 
1. Male or female subjects, 22 years or older.2. Visually significant cataract.3. Diagnosed with mild to moderate open angle glaucoma (e.g. primary open angle glaucoma, pigmentary glaucoma, pseudoexfoliative glaucoma) as documented in subjects' medical record substantiated using funduscopic exam or OCT and at least one visual field test using the SITA Standard 24-2 testing algorithm.4. [REDACTED]5. At baseline, unmedicated diurnal IOP 24-39 mmHg and IOP at least 3 mmHg higher than screening IOP.6. Scheduled for cataract extraction followed by either:
a) ab-interno transluminal viscoelastic delivery with trabeculotomy using OMNI surgical Systemb) ab-interno transluminal viscoelastic delivery using OMNI surgical Systemc) [REDACTED].7. Shaffer grade of \geq III in all four quadrants.8. Potential of good best corrected visual acuity post cataract extraction, in the investigator's judgment9. Able and willing to comply with the protocol, including all follow-up visits.10. Understand and sign the informed consent.
--------------------	---

Exclusion Criteria	
A subject who meets any of the exclusion criteria listed below will not receive the study procedure:
 
 1. Any of the following prior treatments for glaucoma: 
 o Laser trabeculoplasty \leq3 months prior to baseline o Implanted with iStent (All types), Cypass, Xen, Express, glaucoma draining device/valve, or Hydrus Device o Prior canaloplasty, goniotomy, trabeculotomy, trabeculectomy, ECP or CPC 2. Acute angle closure, normal tension, traumatic, congenital, malignant, uveitic, neovascular or severe glaucoma as documented in subjects' medical record. 3. Concurrent IOP-lowering procedure other than one of the study procedures listed under inclusion criterion 6 at the time of cataract surgery (e.g. ECP, CPC, etc.) 4. In the Investigator's judgement, predisposed to significant risk because of washout of ocular hypotensive medications. 5. Concurrent ocular pathology or systemic medical condition which, in the Investigator's judgment, would either place the subject at increased risk of complications, contraindicate surgery, place the subject at risk of significant vision loss during the study period (e.g., wet AMD, corneal edema, Fuch's dystrophy, active intraocular infection or inflammation within 30 days prior to Screening Visit, etc.), or interfere with compliance to elements of the study protocol (e.g., returning to Investigator's office for follow-up visits). 6. History of penetrating keratoplasty or another corneal transplant; corneal abnormality that would prevent reliable IOP measurement; e.g. keratoconus or abnormally thick or thin cornea. 7. BCVA of logMAR 1.0 (20/200) or worse in the fellow eye not due to cataract. 8. Participation (\leq 30 days prior to baseline) in an interventional trial which could have a potential effect on the study outcome, as determined by the study investigator. 9. Women of childbearing potential if they are currently pregnant or intend to become pregnant during the study period; are breast-feeding; or are not in agreement to use adequate birth control methods to prevent pregnancy throughout the study.
---------------------------	---

Number of Subjects Enrolled and Treated	Approximately 459 [REDACTED] to complete 411 [REDACTED] [REDACTED] at 12 months postoperative assuming approximately 10% drop-out rate
Study Duration for each Subject	Up to 40 months
Number of Sites	Up to 30 study sites in US
Schedule of Visits	Screening, Baseline, Surgery (Day 0), Day 1, Week 1, Month 1, 3, 6, 12, 18, 24, 36 Additional post-washout visits will be scheduled for the subjects who are on medications at 12, 24 and 36 months.
Randomization	1:1:1
Treatments	
 • Ab-interno transluminal viscoelastic delivery (up to 360 degrees) and trabeculotomy (at least 180 degrees and up to 360 degrees) using the OMNI Surgical System • Ab-interno transluminal viscoelastic delivery (up to 360 degrees) using the OMNI Surgical System [REDACTED]

2 STUDY OBJECTIVE

First, to prospectively compare the clinical effect of the transluminal viscoelastic delivery and trabeculotomy using the OMNI Surgical System [REDACTED] used with Cataract Extraction in eyes with open angle glaucoma (OAG) and second, to prospectively compare the clinical effect of the transluminal viscoelastic delivery using the OMNI Surgical System [REDACTED] used with Cataract Extraction in eyes with open angle glaucoma (OAG).

3 BACKGROUND AND JUSTIFICATION FOR THE STUDY

Glaucoma is a progressive disease leading to irreversible damage to retinal ganglion cells with the global burden expected to rise to 111.8 million people by the year 2040.¹ OAG is the most prevalent form of glaucoma and it's proven that lowering IOP is the only efficient way to slow down the progressive optic nerve damage and visual field loss.² Hypotensive eye drops are commonly used as the first line clinical management for

¹ Tham YC, Li X, Wong TY, et al. Global prevalence of glaucoma and projections of glaucoma burden through 2040: a systematic review and meta-analysis. *Ophthalmology*. 2014;121:2081–2090.

² European Glaucoma Society. Terminology and guidelines for glaucoma 4th edition Savona, Italy: Editrice PublComm, 2014.

OAG.³ Ocular side effects such as allergies, ocular surface disorders, blepharitis, pemphigoid, abnormal pigmentation etc. and systemic side effects such as bradycardia, headaches, depression, anxiety, confusion, dysarthria, hallucinations, lethargy, polyuria, weight loss, metabolic acidosis, etc. can occur during long term use of topical medications for management of OAG.⁴ There is also a documented low rate of compliance and tolerability with eye drops that results in disease progression and loss of vision.⁵ The cost of these chronic medications and difficulty administering drops to the eyes contributes to poor compliance.

The Ocular Hypertension Treatment Study showed that reduction of IOP by an average of 22.5% through medical intervention decreased conversion from ocular hypertension to glaucoma over a 5-year period to approximately half that of untreated controls (4.4 vs. 9.5%).⁴ Similarly, the EMGT showed that treatment of newly diagnosed primary OAG with argon laser trabeculoplasty plus betaxolol reduced the risk of disease progression at 6 years to half of that for untreated controls (hazard ratio, 0.50; 95% confidence interval, 0.35–0.71).⁶ Each mmHg of IOP reduction decreased the risk of progression by approximately 10%.⁷ AGIS showed that eyes with 100% of visits with IOP less than 18 mmHg over 6 years had mean changes from baseline in visual field defect score close to zero during follow-up.⁷

OAG.¹⁹ Cataract surgery is known to reduce IOP in glaucoma patients. Combined glaucoma and cataract surgery often result in a greater decrease in IOP and use of glaucoma medications compared with cataract surgery alone.^{20,21} When a patient with glaucoma also requires surgical intervention for cataract, the ophthalmologist often performs simultaneous cataract and glaucoma surgery.

Note: A summary of known and potential risks to humans, as identified in the literature or through preclinical testing and/or prior clinical evaluations for the study devices can be found in the Instructions for Use for the OMNI Surgical System [REDACTED]

This prospective, multicenter, randomized controlled, post-market clinical trial will evaluate and compare clinical outcomes of i) ab-interno transluminal viscoelastic delivery and trabeculotomy using OMNI™ Surgical System, ii) ab-interno transluminal viscoelastic delivery using the OMNI™ Surgical System and iii) TM implantation [REDACTED] [REDACTED] in patients with mild to moderate open angle glaucoma undergoing cataract surgery.

4 STUDY DEVICE

4.1 INDICATIONS FOR USE

The OMNI Surgical System has been 510k cleared by the US Food and Drug Administration (FDA) for the following indication for use:

The OMNI® PLUS Surgical System is a manually operated device for delivery of small amounts of viscoelastic fluid, for example Healon® PRO or Healon GV® PRO from Johnson & Johnson Vision, Amvisc® from Bausch & Lomb, or PROVISC® from Alcon, during ophthalmic surgery. It is also indicated to cut trabecular meshwork tissue during trabeculotomy procedures.

4.2 DEVICE DESCRIPTION

The OMNI™ Surgical System (“OMNI”) is a sterile, single use, manually operated instrument used by ophthalmologists to deliver small, controlled amounts of viscoelastic

¹⁹ Bourne RRA, Stevens GA, White RA, et al. Causes of vision loss worldwide, 1990-2010: a systematic analysis. *Lancet Glob Heal.* 2013;1:339-349.

²⁰ Zhang ML, Hirunyachote P, and Jampel H. Combined surgery versus cataract surgery alone for eyes with cataract and glaucoma. *Cochrane Database Syst Rev.* 2015; 7: CD008671

²¹ Vold S, Ahmed II, Craven ER, Mattox C, Stamper R, Packer M, Brown RH, Ianchulev T; CyPass Study Group. Two-Year COMPASS Trial Results: Supraciliary Microstenting with Phacoemulsification in Patients with Open-Angle Glaucoma and Cataracts. *Ophthalmology.* 2016 Oct;123(10):2103-12. doi: 10.1016/j.ophtha.2016.06.032.

[figure not shown]
into the anterior segment of the eye during ophthalmic surgery. It is also indicated to cut trabecular meshwork tissue during trabeculotomy procedures.

The OMNI is designed to function with commonly used viscoelastic fluids made commercially available by companies such as Abbott Medical Optics (AMO), Bausch & Lomb, and Alcon. The OMNI dispenses fluid on the principle of exchanging volumes much like a syringe. The handheld instrument includes a cannula, microcatheter, internal reservoir and plunger tube, and finger wheels. The finger wheels on the handle of the device are used to advance and retract the microcatheter. In addition, when the device is being used to deliver viscoelastic, retraction of the microcatheter causes the plunger tube to advance into the viscoelastic fluid reservoir thereby dispensing viscoelastic fluid.

The microcatheter can be advanced/retracted up to 20 mm per cycle. The microcatheter can be fully advanced/retracted up to 5 times (i.e. 5 full cycles of 20 mm each). Dispensation of viscoelastic can only occur during the first two 20-mm cycles.

The OMNI can deliver approximately 5.5 microliters of viscoelastic in each 20 mm cycle (total volume = 11 microliters). The Plus configuration can deliver approximately 10.5 microliters of viscoelastic in each 20 mm cycle. The total volume of viscoelastic that can be delivered by the OMNI Plus is approximately 21 microliters.

Figure 1: OMNI Surgical System

4.3 TRAINING

Investigators participating in the study must be experienced in using the OMNI 2.0 (OMNI NextGen) Surgical System. All study staff will receive training on the protocol and execution of the study according to applicable regulations and Good Clinical Practices.

5 STUDY DESIGN

This is a prospective, randomized, controlled, multicenter, comparative study in which a total of 459 subjects will be randomized in an equal allocation ratio (1:1:1) to either the OMNI (transluminal viscoelastic delivery AND trabeculotomy), OMNI (transluminal viscoelastic delivery only), or [REDACTED] and followed for 36 months after surgery.

The study will employ a medication washout [REDACTED] [REDACTED] which eliminates the potential confounding influence of ocular hypotensive medications in the assessment of device effectiveness.

5.1 STUDY DEVICES

The study device is the OMNI Surgical System. Subjects randomized to one of the two OMNI treatment groups will undergo either

- Ab-interno transluminal viscoelastic delivery (up to 360 degrees) and trabeculotomy (at least 180 degrees and up to 360 degrees) using the OMNI Surgical System
- Ab-interno transluminal viscoelastic delivery (up to 360 degrees) using the OMNI Surgical System

The Comparator group is the [REDACTED]. [REDACTED] [REDACTED]

5.2 STUDY SITES

This study will be conducted at up to 30 sites in the United States.

6 STUDY ENDPOINTS

6.1 EFFECTIVENESS ENDPOINTS

The **Primary effectiveness endpoint** is:

- Mean change in unmedicated DIOP from baseline at 12-month postoperative examination

Other effectiveness endpoints are:

- Proportion of eyes with a $\geq 20\%$ decrease in **unmedicated** mean diurnal IOP (DIOP) from baseline
- Proportion of eyes with **unmedicated** mean DIOP between 6 and 18 mmHg inclusive
 - Mean change in the number of ocular hypotensive medications compared to Screening
 - Percent change in **unmedicated** DIOP from baseline

6.2 SAFETY ENDPOINTS

Safety will be assessed by evaluating the following measures over time:

- Rates of ocular adverse events (intraoperative, postoperative)
- Reduction in best corrected distance visual acuity (BCVA) from baseline (note: reduction in BCVA due to posterior capsular opacity (PCO) will not be treated as a safety event)
- Secondary Ocular Surgical Interventions, including laser, for IOP control

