7 STUDY SELECTION CRITERIA

7.1 INCLUSION CRITERIA

At least one eye of each participating subject should meet inclusion criteria.

1. Male or female subjects, 22 years or older.
2. Visually significant cataract.
3. Diagnosed with mild to moderate open angle glaucoma (e.g. primary open angle glaucoma, pigmentary glaucoma, pseudoexfoliative glaucoma) as documented in subjects' medical record substantiated using funduscopic exam or OCT and at least one visual field test using the SITA Standard 24-2 testing algorithm.
O [REDACTED]
I [REDACTED]
I [REDACTED]
I [REDACTED]
4. At screening, [REDACTED] on 1-5 IOP-lowering medications (For combination IOP-lowering medications that consist of two or more IOP-lowering drugs, each IOP-lowering drug component counts as a separate medication.) with a stable medication regimen for at least two months prior to screening visit.

5. At baseline, [REDACTED] IOP at least 3 mmHg higher than screening IOP.
6. Scheduled for cataract extraction followed by either:
 - a) ab-interno transluminal viscoelastic delivery with trabeculotomy using OMNI surgical System
 - d) ab-interno transluminal viscoelastic delivery using OMNI surgical System
 - e) [REDACTED]
7. Shaffer grade of \geq III in all four quadrants.
8. Potential of good best corrected visual acuity post cataract extraction, in the investigator's judgment
9. Able and willing to comply with the protocol, including all follow-up visits.
10. Understand and sign the informed consent.

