10.5.2 BEST CORRECTED VISUAL ACUITY (BCVA)

The number and percent of eyes reporting with BCVA of 20/20 or better, 20/25 or better, 20/32 or better, 20/40 or better, worse than 20/40 to 20/80, worse than 20/80 to 20/200, and worse than 20/200 at each visit will be summarized. The number and percent of eyes reporting BCVA of increase \geq 10 letters, increase 10 letters, increase \geq 5 letters to < 10 letters, within 5 letters change, decrease \geq 5 letters to < 10 letters, decrease 10 letters, and decrease \geq 10 letters at each postoperative visit will be calculated.

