19.3 VISUAL ACUITY WITH MANIFEST REFRACTION

ETDRS will be used in testing and documenting subject visual acuity.

ETDRS Testing Method

Best-corrected visual acuity (BCVA) will be tested and scored using the ETDRS system, and will be obtained at the screening and baseline visits for both eyes, and at all scheduled follow-up visits for the study eye only.

The ETDRS chart must be placed at a distance of 4.00 meters (13 feet and 1.5 inches, or 157.5 inches) from cornea to chart surface, when using a 4-meter chart. For the patients unable to read the topmost line of 4.00 meter chart VA should be tested at 1 meter. For testing at 1 meter, the distance must be 1.00 (39 and 3/8 inches).

The 1-meter distance is measured from the eye of the participant, seated comfortably in a chair with his/her back firmly placed against the chair, to the center of the 2nd or 4th letter of the 3rd line of the chart. The measuring device can be homemade (e.g., a dowel rod accurately cut to a length of 1.00 m) or 1 meter ruler may be purchased.

Note: If it is necessary to refract at the 1-meter distance, a +0.75 sphere lens should be added to the trial frame. Subtract the +0.75 sphere from the final refraction obtained at the 1-meter distance before recording the refraction on the form.

Methods

The subject should attempt to read each letter, line-by-line, left to right, beginning with line 1 at the top of the chart. The subjects should be told that the chart has letters only, no numbers. If the subject reads a number, he or she should be reminded that the chart contains no numbers, and the examiner should then request a letter in lieu of the number. The subject should be asked to read slowly, about one letter per second, so as to achieve the best identification of each letter. He/she is not to proceed to the next letter until he/she has given a definite response.

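### The BCVA safety endpoint measures loss from a cataract-affected preoperative baseline, so a moderate later loss within an eye can be offset by the cataract gain; the letter-change bins in 10.5.2 also overlap

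*Combined protocol and SAP*

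**What the plan says.** Section 6.2 lists three safety measures. One is "Reduction in best corrected distance visual acuity (BCVA) from baseline", with the qualification that "reduction in BCVA due to posterior capsular opacity (PCO) will not be treated as a safety event". The Synopsis repeats this endpoint, and the interim analysis in Section 10.6 uses the same reference.

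The visit schedule in the Synopsis is "Screening, Baseline, Surgery (Day 0), Day 1, Week 1, Month 1, 3, 6, 12, 18, 24, 36", so baseline is preoperative. Section 7.1 requires "Visually significant cataract" and also "Potential of good best corrected visual acuity post cataract extraction, in the investigator's judgment". Section 19.3 states that BCVA "will be obtained at the screening and baseline visits for both eyes, and at all scheduled follow-up visits for the study eye only".

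Section 10.5.2 gives two summaries. The first tabulates absolute acuity categories at each visit, from 20/20 or better down to worse than 20/200. The second counts eyes by letter change at each postoperative visit. It does not say what the change is measured from, and its loss rows end with "decrease 10 letters, and decrease" of at least 10 letters. Under Section 10.5 all safety summaries are given for the three study groups separately.

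**The concern.** The eligibility criteria expect acuity to rise after surgery in all three arms, while the endpoint measures loss from the level before that rise. An eye that gains 15 letters and later loses 15 has a net change of zero and is tabulated as stable. The blind spot is moderate loss that develops after recovery and stays smaller than, or close to, the surgical gain. Randomisation balances the expected gain across arms but does not restore the events that are netted out in each arm.

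BCVA reduction is one of three named safety measures, and follow-up runs to Month 36, so the summary should be able to show such loss eye by eye.

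The letter-change rows have a separate fault. As printed they are not mutually exclusive, and the loss side has no row beyond 10 or more letters.

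**Working it through.** **Reference.** The plan gives no figure for expected acuity gain or for a BCVA loss rate, so there is nothing of its own to reproduce. From the documents: the endpoint is change from baseline (6.2, Synopsis, 10.6); baseline precedes surgery (Synopsis); each study eye has a significant cataract and is expected to see well after extraction (7.1). No readable section names a postoperative reference for BCVA loss.

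**Size of the offset (illustration on assumed inputs).** Let the gain from cataract removal be normal with mean G and standard deviation SD, and let the later true loss be L letters. Change from baseline is gain minus L. An eye is flagged at cut c if that change is −c or lower:

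P(flag) = Φ((L − c − G)/SD)

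With L = 15 and SD = 10:

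| Mean gain G | Loss ≥10 from baseline | Loss ≥5 from baseline |
|---|---|---|
| 8 | Φ(−0.3) = 38% | Φ(0.2) = 58% |
| 12 | Φ(−0.7) = 24% | Φ(−0.2) = 42% |
| 16 | Φ(−1.1) = 14% | Φ(−0.6) = 27% |

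For L = 10 at the 10-letter cut, the same gains give Φ(−0.8) = 21%, Φ(−1.2) = 12% and Φ(−1.6) = 5%.

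**Sensitivity to the assumptions** (10-letter cut, SD 5 / 8 / 10):

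- L = 15, G = 0: 84% / 73% / 69%. Most losses are flagged; the shortfall comes from the spread in gain, not its mean.
- L = 15, G = 5: 50% at each SD.
- L = 15, G = 15: 2% / 11% / 16%.
- L = 30, G = 15: 84% / 73% / 69%. Very large losses still mostly show.

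If L = 15 is measured from the postoperative level without measurement error, every such eye meets the 10-letter cut.

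**Bins.** Each whole-letter change from −20 to +20 was placed in the rows of 10.5.2 as printed:

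- +10 falls in both the row for 10 and the row for at least 10; −10 does the same on the loss side.
- +5 and −5 fall in two rows if the middle row (within 5 letters) includes 5, and in one row if it does not.
- No value is left without a row.

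**The case against.** A reader might infer that BCVA loss is judged only against the preoperative baseline, and that the trial therefore has little ability to detect vision loss or a difference between arms. The documents do not support that.

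- Section 10.5.2 also tabulates absolute acuity by visit and, through Section 10.5, by arm. Those categories are not netted against baseline, and in a randomised comparison a difference in postoperative acuity can appear there.
- Ocular adverse events must be recorded whether or not device related (Section 9) and are summarised with confidence intervals (10.5.1). Slit lamp findings and visual field indices are summarised too (10.5.3).
- The list in Section 9.2 is obscured. It could hold a BCVA-loss criterion with its own reference, so its absence cannot be asserted.

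This stands and narrows the point. What remains is that absolute categories are counts per visit, in which opposite movements cancel, and that adverse event capture depends on someone reporting the loss. Neither is a within-eye measure of loss from the postoperative level.

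The illustration is also open to challenge. Its inputs are not in the documents, Section 6.2 sets no 10-letter threshold, and a lower cut flags more eyes; hence the 5-letter column above. At the loosest reading, any reduction at all, a 15-letter loss shows in Φ(0.7) = 76%, Φ(0.3) = 62% and Φ(−0.1) = 46% of eyes for the three gains. A postoperative reference is not perfect either: with symmetric measurement noise, a true 10-letter loss meets a 10-letter cut only about half the time.

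The bin overlap may be a slip in one symbol or an artefact of text extraction. A reader might infer that it spoils the count of larger losses. It does not: the row for at least 10 letters, as printed, still gives the full count. The rows nevertheless cannot be used as a partition, and the intended cut cannot be recovered from the text.

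**Conclusion.** The point holds in a limited form. On the change-from-baseline measure, a moderate later loss within an eye can be offset by the cataract gain, and no readable part of the plan measures loss from the eye's postoperative level. The size depends on the gain, which the documents do not give: substantial at an assumed mean of 8 to 16 letters, half of 15-letter losses missed at the 10-letter cut with a gain of 5, and small if the gain is near zero or the loss very large.

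The overlap at exactly 10 letters is plain in the printed text. The overlap at 5 depends on how the middle row is read. That 10.5.2 does not restate its reference is a matter of fact; that it means baseline is inferred from 6.2.

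BCVA is summarised descriptively, with no test or margin attached. Sample size, significance level and the primary analysis are untouched. This is a worthwhile, cheap improvement to safety reporting, not a defect that undermines the trial.

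**What to change.** In Sections 6.2 and 10.5.2:

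1. Keep change from baseline and the absolute acuity table.
2. State in 10.5.2 what the letter change is measured from.
3. Add, by visit and arm, the number and percent of eyes losing ≥10 and ≥15 letters from one prespecified postoperative reference, either Month 3 BCVA or the best postoperative BCVA to date, with the same PCO exception.
4. Make the letter-change rows mutually exclusive: ≥15, ≥10 to <15, ≥5 to <10, and <5 letters, in each direction.

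The cost is a wording change and one more table from data already collected; no visit or measurement is added. Choosing the reference and cuts before the data are analysed avoids choosing them afterwards.

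There are three downsides to state in the plan. A fixed Month 3 reference misses persistent loss that began before Month 3, because that loss lowers the reference itself, so the added table must be read with the absolute acuity table. Eyes without the reference visit drop out of the added table. Test-retest noise adds some false flags, more so with a best-to-date reference, which tends to pick out favourable readings.
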